5 STUDY ASSESSMENTS

PROs, encompassing HRQoL, treatment satisfaction and elements from EPQ, will be assessed with study Subjects. Tirbanibulin treatment effectiveness and treatment satisfaction will be assessed with Site Investigators. Future treatment preferences will be assessed with both Subjects and Site Investigators. Safety will be evaluated in terms of AEs and ADRs during the treatment period. For pertinent measures, the study respondents will be given an option to indicate “don’t know / not applicable”, especially related to absence of information tied to a missing visit or Subject discontinuation from the study.

5.1 HRQoL Assessments

A combination of a validated questionnaire and an ad hoc questionnaire prepared via modified delphi panel consensus method involving dermatologists, were used for HRQoL assessments.

Skindex-16:

The Skindex 16 consists of 16 items that are classified into three domains: symptoms (four items), emotions, (seven items) and functioning (five items) (Chren 2012; Chren et al, 2001). The following questions (items) correspond to each subscale:

Scale	Items
Symptoms	1-4
Emotions	5-11
Functioning	12-16

All items are scored on a seven-point adjectival response scale, with a potential score of 0 to 6. A domain score is the average of all items within the domain and transformed to a linear scale of 100 varying from 0 (never bothered) to 100 (always bothered). The higher the score, the more severe is the impairment. The questionnaire will be administered in entirety, at baseline and at Week 8 post-index date.

5.2 Treatment Satisfaction Assessments

5.2.3 Study Subject Treatment Satisfaction Assessments

Treatment Satisfaction Questionnaire for Medication (TSQM-9) will be used to assess the treatment satisfaction of Subjects at Weeks 8 & 24 for all patients, in relation to the tirbanibulin treatment they received at the beginning of the study. TSQM-9 will measure patient satisfaction with treatment on three key domains, namely, effectiveness, convenience, and global satisfaction. The following questions (items) correspond to each subscale:

Scale	Items
Effectiveness	1-3
Convenience	4-6
Global satisfaction	7-9

Most items are scored on a 7-point Likert scale of: 1: very dissatisfied; 2: moderately dissatisfied; 3: slightly dissatisfied; 4: neutral; 5: slightly satisfied; 6: moderately satisfied; 7: very satisfied. Items 7 and 8 of TSQM-9 are scored on a 5-point scale of: 1: not at all confident/certain; 2: a little confident/certain; 3: somewhat confident/certain; 4: very confident/certain; 5: extremely confident/certain. TSQM subscale scores will be computed per tool owner specifications and transformed to scores ranging from 0 to 100, with higher scores representing higher satisfaction on respective domains. The TSQM-9 questionnaire will be administered in entirety, at Weeks 8, and 24 post-index date.

The TSQM-9 questionnaire will also be administered at Week 24 among Subjects who are retreated with tirbanibulin in the past 16 weeks (since Week 8 visit), to solicit their satisfaction with the most recent course of tirbanibulin treatment.

Subject's rating (at Weeks 8 & 24) of their satisfaction with the ability of tirbanibulin treatment to 'improve how their skin looks' and 'improve their skin texture' respectively, in the original treated area will be assessed. The responses will be solicited on the following 7-point Likert scale: 1: very dissatisfied; 2: moderately dissatisfied; 3: slightly dissatisfied; 4: neutral; 5:

slightly satisfied; 6: moderately satisfied; 7: very satisfied. These two EPQ items will also be administered at Week 24 again among Subjects who are retreated with tirbanibulin between Week-8 and Week-24 visits, to solicit their satisfaction with the respective attributes associated with the most recent course of tirbanibulin treatment.

Subject's rating of their 'overall satisfaction' with tirbanibulin treatment, in comparison to other topical treatment(s) will be assessed using a 5-point Likert scale of: 1: much worse; 2: somewhat worse; 3: same; 4: somewhat better; 5: much better. This 'overall satisfaction' assessment will be conducted among two Subject subgroups:

- Among Subjects who have experienced other topical treatments before start of tirbanibulin at baseline: At Week 8, compare rating of tirbanibulin treatment vs. previous topical treatment(s).
- Among Subjects who have been retreated with other topical treatments (other than tirbanibulin) between Week-8 and Week-24 visits: At Week 24, compare rating of original tirbanibulin treatment (at beginning of the study) vs. most recent topical treatment(s).

To complement the overall satisfaction question, factors associated with Subject's satisfaction rating will be assessed.

5.2.1 *Site Investigator Treatment Satisfaction Assessments*

An ad hoc satisfaction questionnaire very similar to TSQM-9 will be used to assess Site Investigators' satisfaction with tirbanibulin treatment at Weeks 8 & 24, in relation to the tirbanibulin treatment they administered to Subjects at the beginning of the study. The individual item and subscale scorings will be done similar to the original TSQM-9 questionnaire.

The same ad hoc questionnaire will also be administered at Week 24 among Site Investigators managing Subjects who are retreated with tirbanibulin in the past 16 weeks (since Week 8 visit), to solicit their satisfaction with the most recent course of tirbanibulin treatment.

Site Investigator's rating (at Weeks 8 & 24) of their satisfaction with the ability of tirbanibulin treatment to 'improve how their patient's skin looks' and 'improve their patient's skin texture' respectively, in the original treated area will be assessed. The responses will be solicited on the following 7-point Likert scale: 1: very dissatisfied; 2: moderately dissatisfied; 3: slightly dissatisfied; 4: neutral; 5: slightly satisfied; 6: moderately satisfied; 7: very satisfied. These two EPQ items will also be administered at Week 24 again among Subjects who are retreated with tirbanibulin between Week-8 and Week-24 visits, to solicit their satisfaction with the respective attributes associated with the most recent course of tirbanibulin treatment.

Site Investigator's rating of their 'overall satisfaction' with tirbanibulin treatment, in comparison to other topical treatment(s) will be assessed using a 5-point Likert scale of: 1: much worse; 2: somewhat worse; 3: same; 4: somewhat better; 5: much better. This 'overall satisfaction' assessment will be conducted among two Subject subgroups:

- Among Subjects who have experienced other topical treatments before start of tirbanibulin at baseline: At Week 8, compare rating of tirbanibulin treatment vs. previous topical treatment(s).
- Among Subjects who have been retreated with other topical treatments (other than tirbanibulin) between Week-8 and Week-24 visits: At Week 24, compare rating of original tirbanibulin treatment (at beginning of the study) vs. most recent topical treatment(s).

To complement the overall satisfaction question, factors associated with Site Investigator's satisfaction rating will be assessed.

5.3 Treatment Effectiveness Assessments

The effectiveness of tirbanibulin treatment will be assessed from the perspective of Site Investigators as well as the Subjects. It is expected that the Site Investigator assessments will be conducted via in-person visits/encounters at baseline, Week 8 and Week 24, and when in-person assessments are not feasible (owing to COVID-related travel restrictions), the assessments

maybe done via virtual/remote visits. The same evaluator at study site shall perform all evaluations for a subject during the study, as feasible.

5.3.1 *Investigator Global Assessment (IGA):*

Site Investigators to assess the status of subject's AK in the treated area on the face or scalp using the following IGA scale, at Weeks 8 and 24. The IGA should be representative of the investigator's overall general assessment of the subject's AK and take into account the quality, as well as the quantity, of AK lesions.

Outcome Measure	Score
Completely cleared - Approximately 100% clearance of AK lesions in the treated area	0
Partially cleared - Approximately $\geq 75\%$ clearance of AK lesions in the treated area	1
Moderately cleared - Approximately 50-74% clearance of AK lesions in the treated area	2
Minimally Cleared - Approximately <50% clearance of AK lesions in the treated area	3
Not Cleared - Approximately 0% clearance, i.e., all AK lesions remained in the treated area	4

5.3.2 *Severity of Skin Photodamage*

Site Investigators will be asked to rate the severity of skin photodamage in the AK treated area (at baseline, Weeks 8 and 24), on the following 4-point Likert scale:

Outcome Measure	Score
Absent - Smooth evenly pigmented skin	0
Mild - Freckling and/or other dyspigmentation	1
Moderate - Above plus mildly rough "dry" skin, fine wrinkling and/or telangiectasias or blotchy erythema	2

Severe - Above plus pronounced “dryness” and/or dyspigmentation and/or telangiectasia or erythema, and/or wrinkling, with or without areas of actinic purpura	3
---	---

5.3.3 Cosmetic Appearance of Skin

Subjects and Site Investigators will be asked to rate current ‘overall appearance of the skin’ in the AK treated area (at Weeks 8 and 24, in comparison to baseline), on the following 5-point Likert scale: 1: much worse; 2: somewhat worse; 3: no change; 4: somewhat improved; 5: much improved.

Subjects will be asked to state how often has he/she been bothered by the appearance of the skin, at Baseline and Week 8, using item # 7 in Skindex-16 questionnaire. This item however will not be analyzed individually but assessed as part of emotions subscale of Skindex-16.

5.3.4 Study Subject Qualitative Narratives

All subjects from one (1) study site will be asked to record a 1-3 minute audio (using the Mobile App) narrating their perceptions of treatment benefits associated with the tirbanibulin, at Week 8. This qualitative data will be used to ascertain attributes that study Subjects associate with tirbanibulin treatment in an un-prompted manner.

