7.5 AK Photography & Subject Insights

In a small subset of sites (up to 2), Site Investigators will utilize Canfield® photography equipment to take photographs of Subject's AK treated area in the face or scalp to visually capture the clinical status of AK at baseline (study entry) and at Weeks 1, 2, 4 and 8, and will document their assessment/grading of LSR. In addition to the baseline and Week-8 encounters, Subjects at these sites will hence be consented to undertake additional in-person visits at Weeks 1, 2 & 4. At Week 8, the Subjects from these sites will also be asked to record a 1-3 minute audio narrating their perceptions of treatment benefits associated with the tirbanibulin.

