14.3 Informed Consent Process

Informed consent is a process that is initiated prior to the individual agreeing to participate in the study and continues throughout study participation.

The participating Site Investigator will ensure that written informed consent is obtained from each adult Subject in accordance with applicable regulations. Study Subjects may provide consent using online data collection portal. Each subject will provide informed consent prior to participating in any study procedures, as outlined in Section 6.3.2 of this protocol. As an addendum to the main consent form, the Subjects from a small subset of sites will be consented to allow photographs of their face/scalp taken at baseline, and Weeks 1, 2, 4 and 8 by their clinician at the privacy of the clinician's office, and will be consented to provide a 1-3 minute testimonial of Subject's experience with tirbanibulin at Week 8.

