14.4 Participant Confidentiality

Participant confidentiality is strictly held in trust by the investigators, study staff, and the sponsor(s) and their agents. The final research data will constitute only **de-identified** data, for research analyses and reporting. Participants will be identified by a unique study ID number assigned by the site coordinator and/or study CRO, which will be listed on the paper-based consent forms or online e-consent forms and on each of the online e-DCFs. The site coordinator and the CRO project team may review the e-DCFs for any missing data periodically. Access to the online e-DCFs will be restricted to the patient/caregiver, the site coordinator/Investigator, and the relevant representatives from the CRO.

The study protocol, documentation, data, and all other information generated will be held in strict confidence. Site Investigator and study subject contact information will be collected strictly for administrative purposes, such as processing of incentives and to share study follow-up reminders. This personally identifiable information will remain separate from research data.

Photographs to document AK clinical status at baseline and Weeks 1, 2, 4 and 8 will be obtained from a small subset of study Subjects. Audio testimonials depicting Subject's experience with tirbanibulin may be obtained from the same subset of study Subjects at Week 8. All of these data

will be stored electronically and anonymized (using appropriate digital technology) before using this data for further analyses and/or publications.

No information concerning the study or the data will be released to any unauthorized third party without prior written approval of the sponsor or the study CRO. The study CRO or other authorized representatives of the sponsor may inspect all study documents and records, but at no juncture will study subject identifiable information will be collected or disclosed.

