5.4.3 Perceptions of LSRs

The following three assessments will be conducted at Week-8 for Subjects who have experienced other topical treatments before start of tirbanibulin at baseline, and at Week-24 for Subjects who have been treated with other topical treatments (other than tirbanibulin) between Week-8 and Week-24 visits:

- Subjects and Site Investigators will be asked to rate the ‘duration of skin reactions’ associated with tirbanibulin, in comparison to other topical treatments (previous or most recent retreatment). The relative assessment will be based on a 5-point Likert scale of: 1: much longer; 2: somewhat longer; 3: the same; 4: somewhat shorter; 5: much shorter.
- Subjects and Site Investigators will be asked to rate the ‘severity of skin reactions’ associated with tirbanibulin, in comparison to other topical treatments (previous or most recent retreatment). The relative assessment will be based on a 5-point Likert scale of: 1: much worse; 2: somewhat worse; 3: the same; 4: somewhat better; 5: much better.
- Subjects will be asked to rate the ‘impact on their daily activities due to skin reactions’ associated with tirbanibulin use, in comparison to other topical treatments (previous or

most recent retreatment). The relative assessment will be based on a 5-point Likert scale of: 1: much worse; 2: somewhat worse; 3: the same; 4: somewhat better; 5: much better.

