Each AE, either serious or non-serious for which a causal relationship to tirbanibulin cannot be excluded, will be considered as an ADR. An ADR is an injury caused by taking medication. ADRs may occur following a single dose or prolonged administration of a medicinal product or result from the combination of two or more medicinal products. LSRs (such as: erythema, flaking/scaling, crusting, swelling, vesiculation/pustulation, and erosion/ulceration), skin scarring and pigmentation (such as: hypo- and hyper-pigmentation) as a result of application of tirbanibulin in AK treatment area will not be considered as ADRs, but will be documented separately.

The determination of whether an AE is related to study treatment (tirbanibulin) will be based on information regarding the degree to which the study treatment had caused or contributed to the event and will be categorized per the following criteria:

- Related: There were good reasons and sufficient information (e.g. plausible time sequence, dose-response relationship, pharmacology, positive de-challenge and/or re-challenge) to assume a causal relationship with the study medication in the sense that it is plausible, conceivable or likely.
- Not Related: There were good reasons and sufficient information (e.g. implausible time sequence and/or attributable to concurrent disease or other drugs) to rule out a causal relationship with the study medication.

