8 PATIENT QUALITATIVE INPUT FROM SITE AK01

Table summarizing verbatims from audio-input from patients at end of study from Site # AK01 will be added here.

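### The audio task asks patients for treatment benefits, so it cannot show what they associate with tirbanibulin un-prompted; unfavourable attributes are not elicited and are likely under-represented

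*SAP*

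**What the plan says.** SAP 5.3.4 has two sentences. The first asks all subjects at one site to make a recording of 1 to 3 minutes in the mobile app, "narrating their perceptions of treatment benefits associated with the tirbanibulin, at Week 8". The second gives the purpose: "This qualitative data will be used to ascertain attributes that study Subjects associate with tirbanibulin treatment in an un-prompted manner". Protocol 8.3.4 contains the same pair of statements for up to two sites, and Protocol 7.5 repeats the task: "narrating their perceptions of treatment benefits associated with the tirbanibulin".

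Two other protocol sections describe the same recording differently. Section 14.3, on consent, calls it a "testimonial of Subject's experience with tirbanibulin at Week 8". Section 14.4, on confidentiality, says "Audio testimonials depicting Subject's experience with tirbanibulin may be obtained", and foresees that the anonymised material may be used in analyses and publications.

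The only reporting text is in SAP 8: "Table summarizing verbatims from audio-input from patients at end of study from Site # AK01 will be added here". It gives no coding frame and no rule for selecting or dropping remarks.

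**The concern.** The task names benefits. The stated purpose names attributes, which is a wider word, and claims they will emerge without prompting. A patient asked to talk about benefits has been told which half of the experience to describe, so the plan claims a property that its own request does not have.

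The missing half matters in this indication. The background in Protocol 2.1 reports that earlier patient interviews highlighted the effect of local skin reactions on quality of life, daily activities and satisfaction. In the closed list of factors behind overall satisfaction (SAP Table 1.23), three of the eight named options concern local skin reactions: how long they take to resolve, their number and type, and their severity. The study therefore already treats unfavourable attributes as part of what patients associate with treatment.

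If the purpose sentence is carried into a report or publication, readers could take benefits named on request for spontaneous opinion.

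**Working it through.** The plan gives no figure for the narratives beyond the number of sites, so the check is mainly a comparison of texts.

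**1. The request.** SAP 5.3.4, Protocol 8.3.4 and Protocol 7.5 all describe the task as narrating benefits. None mentions skin reactions, burden or lack of effect.

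**2. The purpose.** SAP 5.3.4 and Protocol 8.3.4 say the data will ascertain attributes, with no direction stated, and that these will be un-prompted. Protocol 7.5 gives no purpose.

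**3. The consent description.** Protocol 14.3 and 14.4 speak of experience. Testimonial is not a wholly neutral word, but experience is not limited to benefits. The protocol therefore gives two descriptions of one recording, and they need reconciling whichever was intended.

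**4. Does the request fit the purpose?** Un-prompted could mean either of two things:

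- *Un-prompted as to which attributes are named.* Free speech meets this, in contrast to the tick-list in SAP Table 1.23.
- *Un-prompted as to direction, favourable or unfavourable.* A benefits request does not meet this.

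The purpose sentence does not restrict itself to the first meaning, so it does not hold as written.

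**5. What follows for unfavourable remarks?** They are not asked for, so under-representation is the reasonable expectation. The recording is open speech, however, and no text stops a patient volunteering a negative remark or removes it from the SAP 8 table. Under-represented is supported; excluded is not.

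**6. How many patients?** Inputs: at most 25 subjects per site (Protocol 6.3.2), about 300 subjects in total (Protocol 6 and 12.1), one site in SAP 5.3.4 and up to two in Protocol 8.3.4.

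- One site: 25 / 300 = 8.3%.
- Two sites: (2 × 25) / 300 = 50 / 300 = 16.7%.

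These are ceilings on who could make a recording. They do not measure bias, and the enrolment of Site AK01 is not given.

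**7. Does it reach an endpoint?** The narratives are not among the endpoints listed in Protocol 3.2 and SAP 2.2, and SAP 6 has no analysis subsection for them.

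**The case against.** Four objections deserve weight.

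*Un-prompted may simply mean without a list.* This is plausible, because SAP Tables 1.23 to 1.25 use fixed lists and rankings for the same subject matter. It turns a flat contradiction into loose wording. It does not remove the problem, because the direction of the answer is still supplied. If this was the meaning, the text should say so.

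*The actual prompt is not visible.* The three sections describe the task; they do not quote the app screen, and the prompt is not among the select questionnaires in Appendix B. Patients may have been asked for their experience, as Protocol 14.3 and 14.4 suggest. This stands as a limit: the point rests on how the plan describes the request.

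*Benefits may be what was wanted.* The narratives sit under treatment effectiveness in SAP 5.3. If so, the accurate description is benefits named on request.

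*Negative experience is collected elsewhere.* This is true. The comparative items on severity of skin reactions and impact on daily activities run "1: much worse; 2: somewhat worse; 3: the same; 4: somewhat better; 5: much better". TSQM-9 has dissatisfied options. Local skin reactions, scarring and pigmentation changes "will not be considered as ADRs, but will be documented separately", and the SAP 7.4 tables report them alongside adverse events. The narratives are not the study's source on harm or burden, which limits the consequence. It does not make this particular summary un-prompted.

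**Conclusion.** The point holds as a mismatch between a request and the use claimed for it. As described, the task does not elicit unfavourable attributes, and the SAP 8 summary cannot support a conclusion about what patients associate with tirbanibulin un-prompted. It is minor: a supplementary, descriptive item covering at most 8.3% of patients under the SAP or 16.7% under the protocol.

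A reader might infer three stronger things that the documents do not support:

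- That negative experience is excluded by the question. Open speech and the absence of any rule dropping remarks argue against this.
- That the recordings will be reported as un-prompted opinion. The word appears only in the purpose sentence; the planned table in SAP 8 carries no such label.
- That the summary will be almost wholly favourable whatever patients experienced. No figure in the documents bears on how often patients would volunteer negative remarks, so the extent of under-representation cannot be stated.

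The conclusion assumes that the request patients saw matches the description in SAP 5.3.4 and Protocol 7.5 and 8.3.4. If the app asked for experience, the elicitation problem falls away, and the remaining task is to correct those three sections.

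**What to change.** First establish what the app asked and whether recordings have been made. The SAP gives a safety cohort of 300 and uses the past tense in places (sections 3.2 and 5.1), so enrolment may already be complete; the documents do not say so outright.

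*If recordings are still to be made:* change the request in Protocol 7.5 and 8.3.4, SAP 5.3.4 and the app to match the consent description, for example asking patients to describe their experience with the treatment, good or bad. In SAP 8, summarise favourable and unfavourable mentions separately.

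*If recordings already exist under a benefits request:* delete the un-prompted claim from the purpose sentence, title the SAP 8 table as benefits named when patients were asked for benefits, and state beneath it that negative experience was not asked for.

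The first route costs wording changes to the app, protocol and SAP, with IRB approval of the amendment before it takes effect (Protocol 14.2), and the summary may look less favourable. The second costs a sentence, a table title and a footnote, and gives up the claim of spontaneity.
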